## Secondary End points

COLOVISION Protocol v1.0 18/08/2022 IRAS ID: 313559 Polyp detection rate (PDR) in both groups

Adenoma per colon (APC) in both groups

PIVI-1: agreement between surveillance interval decisions based on histology and that based on the combination of histology of non-diminutive polyps and optical diagnosis in both arms

Diagnostic performance measures in both groups (sensitivity, specificity, accuracy, NPV, PPV, AUC)

Diagnostic performance measures in both groups (sensitivity, specificity, accuracy, NPV, PPV, AUC) according to endoscopists experience

Diagnostic performance measures in both groups (sensitivity, specificity, accuracy, NPV, PPV, AUC) according to endoscopy imaging mode (WLI or EI)

The proportion of histological assessments that could have been avoided in both arms

The proportion of polyp removals that could have been avoided in both arms

Withdrawal time in both groups

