## 10. SAMPLING

- This is powered as a superiority trial.
- For computer aided detection, the ADR of competent but non-expert endoscopists is assumed to be 20% and we believe that CADe will increase it to 30% (expert level). In order to demonstrate a difference of 10% between the two groups with an 80% power and a significance level (alpha) 0.05; we will need 588 patients (294 per group). We will over recruit by 10% (max total of 654) to allow for drop outs, poor bowel prep, incomplete dataset etc. Interim analysis will be done after 50% recruitment
- For computer aided diagnosis, the NPV of endoscopists is assumed to be 75%, and we believe the NPV of endoscopist plus CADx will be 90%. To achieve this with an 80% power and significance level (alpha) of 0.05, we will need to assess 200 diminutive recto-sigmoid (100 per group) polyps (588 total polyps), in an estimated 168 patients. We will plan to over recruit by 10% to allow for incomplete data (220 diminutive recto-sigmoid polyps, 647 total polyps). Interim analysis will be done after 50% recruitment

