### 11.3 Randomisation

Participants will be randomised electronically in a 1:1 ratio into two groups. The intervention group will have their colonoscopy performed with the assistance of the WISE VISION® CAD system, the control arm will have standard colonoscopy. Randomisation will be carried out prior to the procedure being started. The randomisation will be stratified by site to ensure an equal allocation in each centre. Additionally, a blocked randomisation, with varying block sizes, will be performed to allow for a balance between groups throughout the trial.

The randomisation process will be managed using the built-in module within the project's REDCap eCRF database managed by Portsmouth Hospitals University NHS Trust. The Data Manager will generate the randomisation allocation table using statistical software, which will then be uploaded into REDCap before the first patient is consented.

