#### 14.2 Analysis of Endpoints

The primary outcome, ADR, will be compared between groups using the Chi-square test. The difference in the proportion of patients with an adenoma detected between groups will be quantified, along with a corresponding 95% confidence interval.

Within both groups, a descriptive analysis of percentage of polyps correctly identified, relative to the histological diagnosis, will be reported.

For all detection outcomes, a series of sensitivity analyses will be performed, repeating the analyses, but this time only considering polyps in the CAD intervention group if they were correctly identified based on their histology.

Binary secondary outcomes will be analysed using the Chi-square test. Continuous secondary outcomes will be compared between groups using the unpaired t-test, if found to be normally distributed, or the Mann-Whitney test otherwise.

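### Section 14.2 names a plain Chi-square test for all binary secondary outcomes, including polyp-level ones; used between arms, it ignores that polyps cluster within randomised patients

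*Protocol*

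**What the plan says.** Section 14.2 (Analysis of Endpoints) gives one rule for this class of outcome: "Binary secondary outcomes will be analysed using the Chi-square test". It makes no exception for outcomes counted per polyp.

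The secondary endpoints in section 8.2 include "Diagnostic performance measures in both groups (sensitivity, specificity, accuracy, NPV, PPV, AUC"), repeated by endoscopist experience and by imaging mode. They also include the proportion of avoidable histological assessments and "The proportion of polyp removals that could have been avoided in both arms". Polyp detection rate and PIVI-1 are on the same list. The first is a patient-level outcome, and the second is too if it is counted per patient.

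Section 11.3 sets the unit of allocation: "Participants will be randomised electronically in a 1:1 ratio into two groups". Section 10 gives the expected yield for the characterisation part: "polyps (588 total polyps), in an estimated 168 patients".

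Section 14.2 also has a separate sentence on polyp-level correctness: "Within both groups, a descriptive analysis of percentage of polyps correctly identified, relative to the histological diagnosis, will be reported". The protocol nowhere mentions correlation between polyps of one patient, a cluster-robust method or a patient-level summary.

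**The concern.** A Chi-square test on a two-by-two table of polyps treats each polyp as an independent observation. Polyps found in one patient share the procedure, the endoscopist and the bowel preparation, so correct and incorrect diagnoses may tend to run together within patients. Because the patient is randomised, all of that patient's polyps fall in the same arm. Positive correlation therefore adds to the variance of the difference between arms, and the Chi-square test does not count the addition.

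At stake is the credibility of the secondary characterisation results. A difference in accuracy or specificity between arms could be declared significant more often than the nominal 5% when there is no difference. The protocol does not simply leave the method to a later analysis plan. It names a test whose independence assumption its own design does not meet.

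**Working it through.** **Inputs from the protocol.** Section 10: 588 polyps in total, 200 of them diminutive rectosigmoid, in 168 patients; NPV 75% versus 90%; power 80%; alpha 0.05. Section 11.3: 1:1 randomisation of participants.

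**Inputs assumed.** The intraclass correlation (ICC) within patients is not given; 0.1 to 0.3 is used as a range. The share of polyps entering each measure is not given; one half is used as an illustration.

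**1. The protocol's own figure.** Section 10 states: "To achieve this with an 80% power and significance level (alpha) of 0.05, we will need to assess 200 diminutive recto-sigmoid (100 per group"). The usual formula for two independent proportions, two-sided and without continuity correction, is

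n = [1.96·√(2·p̄·(1−p̄)) + 0.8416·√(p₁(1−p₁) + p₂(1−p₂))]² / (p₁−p₂)².

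With p₁ = 0.75, p₂ = 0.90 and p̄ = 0.825:

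n = [1.96·√0.28875 + 0.8416·√0.2775]² / 0.0225 = 99.5, so 100 per group (power 80.2%).

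The stated size is reproduced, and it rests on independent polyps. This shows the planning assumption only; the NPV it refers to is the primary endpoint, which is not the subject here.

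**2. Polyps per patient.** All polyps: 588/168 = 3.5. Half the polyps: 1.75. Diminutive rectosigmoid polyps: 200/168 = 1.19.

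**3. Design effect and true level, equal counts per patient.** DE = 1 + (m−1)·ICC. True level of a nominal 5% test = 2·[1 − Φ(1.96/√DE)].

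| Polyps per patient (m) | ICC 0.1 | ICC 0.2 | ICC 0.3 |
|---|---|---|---|
| 3.5 (accuracy) | DE 1.25, level 8.0% | DE 1.50, level 11.0% | DE 1.75, level 13.8% |
| 1.75 (half the polyps, assumed) | DE 1.075, level 5.9% | DE 1.15, level 6.8% | DE 1.225, level 7.7% |
| 1.19 (diminutive rectosigmoid) | DE 1.02, level 5.2% | DE 1.04, level 5.4% | DE 1.06, level 5.7% |

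**4. Unequal counts.** The uncorrected Chi-square test was simulated under no difference: 84 patients per arm, mean 3.5 polyps, beta-binomial correctness around 80%, 20,000 runs. With counts of one plus a Poisson variable the level was 9.1%, 12.7% and 16.4% at ICC 0.1, 0.2 and 0.3. With geometric counts it was 11.0%, 16.7% and 21.8%. At ICC 0 the two versions gave 5.0% and 5.3%, so the excess comes from the clustering. The protocol gives no count distribution, so these figures show direction and order of size only.

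For the diminutive rectosigmoid polyps, a coefficient of variation of 0.5 in the counts gives 5.6%, 6.1% and 6.7%, from DE = 1 + [m(1+CV²)−1]·ICC. The closeness to 5% therefore depends on counts not varying widely.

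**5. Width of intervals once clustering is allowed for.** Standard errors scale with √DE. For all-polyp measures √1.25 = 1.12 and √1.75 = 1.32, so intervals are 12% to 32% wider.

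**The case against.** The strongest objection is that the protocol may not intend to test the diagnostic measures at all. Its one explicit sentence on polyp-level correctness is descriptive and within group, and the Chi-square sentence fits patient-level outcomes such as polyp detection rate without difficulty. This stands in part. The descriptive item carries no test and is outside this point, and the conclusion has to be conditional on the measures being compared between arms. It does not dispose of the matter: the descriptive sentence covers only the percentage correctly identified, whereas section 8.2 lists the diagnostic measures as secondary endpoints and section 14.2 assigns the Chi-square test to binary secondary outcomes without exception.

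A second objection concerns size, and it stands. The 3.5 polyps per patient is the full denominator only for a measure such as accuracy. Sensitivity uses adenomas, specificity non-adenomas, and NPV and PPV only polyps given the corresponding call. Their inflation is smaller.

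Third, a reader might infer that comparisons between imaging modes or experience levels are also anti-conservative. The protocol does not support that. It lists performance in both groups according to these factors and states no test between their levels. If the mode varies within a patient, the inflation need not occur. A simulation with 168 patients and the same ICC range gave about 5% with mode assigned at random per polyp, and about 4%, 3% and 2% with mode split evenly within patients.

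Finally, handling of clustering is often left to an analysis plan. That would answer silence, but here the protocol has already named the test.

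**Conclusion.** The point holds for between-arm comparisons of polyp-level binary secondary outcomes. As section 14.2 is written, any positive within-patient correlation makes their p-values too small. With equal counts and an assumed ICC of 0.1 to 0.3, the true level of a nominal 5% test is about 8% to 14% for accuracy, about 6% to 8% for measures using roughly half the polyps, and close to 5% for the diminutive rectosigmoid subset. It is higher where counts vary between patients. The principle is secure; the size rests on an ICC, a count distribution and denominators that the protocol does not give.

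The point does not extend to ADR or polyp detection rate, which are counted per patient, or to AUC, which is not a binary outcome. Nor should a reader infer that the co-primary conclusion is undermined: PIVI-2 NPV is not a secondary outcome, so the quoted sentence does not govern it.

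**What to change.** In section 14.2, limit the Chi-square test to patient-level binary outcomes, such as polyp detection rate, and PIVI-1 if it is counted per patient. For between-arm comparisons of polyp-level or specimen-level binary outcomes, name one of the following:

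- a logistic GEE with patient as the cluster and robust standard errors;
- a mixed logistic model with a patient random effect;
- a patient-level cluster bootstrap for the difference in proportions.

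Include site as a covariate in the model-based options, since randomisation is stratified by site. Add a sensitivity analysis that also allows for endoscopist, because clustering on patient alone does not capture correlation between patients examined by the same endoscopist. If some of the diagnostic measures are meant to be descriptive only, say which.

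The cost is analysis wording. No further patients or visits are needed, and section 11.4 already has each polyp and the endoscopist recorded. Intervals for all-polyp measures become about 12% to 32% wider at ICC 0.1 to 0.3, and less so for measures with fewer polyps per patient.

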	
 
To evaluate the impact of the CAD system on real time characterisation (optical diagnosis) of polyps compared to histology.
 
				
Secondary Objectives	To evaluate the effect of the CAD device on other polyp detection parameters.				
Primary Endpoints	Adenoma detection rate in both groups PIVI-2: NPV of adenoma diagnosis in diminutive (<5mm) rectosigmoid polyps in both groups				
Secondary Endpoints	Polyp detection rate (PDR) in both groups Adenoma per colon (APC) in both groups PIVI-1: agreement between surveillance interval decisions based on histology and that based on the combination of histology of non- diminutive polyps and optical diagnosis in both arms Diagnostic performance measures in both groups (sensitivity, specificity, accuracy, NPV, PPV, AUC) according to various factors (eg endoscopist's experience) Withdrawal time in both groups				
Intervention (s)	Colonoscopy plus WISE VISION® CAD device				

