## 11.4 Study Assessments

Baseline characteristics will be recorded for all participants. Basic demographics will be recorded to include:

- Age
- Sex
- Co-morbidities and ASA score
- History of previous polyps/bowel conditions

During the colonoscopy the following will be recorded in all patients:

- Endoscopist including level of experience (number of life time procedures)
- Indication
- Bowel preparation used and quality
- Use of sedation/general anaesthetic
- Procedure start and finish time and time of maximal intubation
- Comfort score
- Adverse events
- Polyps detected to include the endoscopists optical diagnosis and assessment of size, morphology using the Paris classification, site and details of their removal.
- Still image/video of polyp (where available)

For patients randomised to colonoscopy plus CAD the following additional data will be recorded:

- Total number of potential polyps identified by CADe
- CADx diagnosis of polyps identified
- Outcome of assessment by endoscopist e.g. confirmed as polyp, characterisation assessment

Post colonoscopy:

- Adverse events will be recorded
- Histology of any polyps removed will be recorded to correlate with the endoscopist/CADx assessment of the lesion.

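### The blanket Chi-square rule does not suit diagnostic performance by endoscopist experience: it treats polyps as independent and contains no arm-by-experience comparison

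*Protocol*

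**What the plan says.** Section 8.2 of the protocol lists as a secondary endpoint: "Diagnostic performance measures in both groups (sensitivity, specificity, accuracy, NPV, PPV, AUC) according to endoscopists experience". The synopsis has the same item, with experience as an example: "according to various factors (eg endoscopist's experience"). Section 11.4 shows how experience is captured, as an attribute of the operator: "Endoscopist including level of experience (number of life time procedures"). No cut-points are given.

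For the analysis, Section 14.2 has one general sentence: "Binary secondary outcomes will be analysed using the Chi-square test". It names no unit of analysis, clustering adjustment, regression model or interaction term. The same section also has a descriptive sentence: "Within both groups, a descriptive analysis of percentage of polyps correctly identified, relative to the histological diagnosis, will be reported".

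The only unit stated for the CADx part is the polyp. Section 10 sizes it at 200 diminutive rectosigmoid polyps, described as "100 per group) polyps (588 total polyps), in an estimated 168 patients".

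**The concern.** Each optical diagnosis behind sensitivity, specificity, accuracy, NPV and PPV is right or wrong, so these measures fall under the binary rule. AUC does not. For the measures that do, the rule can be applied in two ways, and neither answers the question that the endpoint poses.

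- **Experience levels compared with each other.** All polyps read by one endoscopist share the same experience value, so the independent units are the endoscopists. A Chi-square on polyps overstates the information and rejects too often.
- **Arms compared within each level.** Each test asks whether the arms differ in that level. Two such tests side by side do not test whether the CADx effect differs between levels.

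At stake is a statement in the trial report about which endoscopists read better, or which benefit from CADx, resting on a p-value that does not support it.

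**Working it through.** **Inputs from the protocol.** Section 10: NPV 75% v 90%, power 80%, alpha 0.05 (sidedness not stated), 100 diminutive rectosigmoid polyps per group, 588 polyps in total, about 168 patients. Section 9.1: seven sites.

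**Assumed, because the protocol gives no figure.** 14-28 endoscopists (2-4 at each of 7 sites), endoscopist ICC 0.02-0.10, two experience levels of equal size, endoscopists working in both arms.

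**Step 1: the plan's own figure.** With two-sided alpha and pooled variance, n per group = [1.96 × √(2 × 0.825 × 0.175) + 0.8416 × √(0.75 × 0.25 + 0.90 × 0.10)]² / 0.15² = 99.5, so 100. The stated 200 polyps reproduce. The formula treats polyps as independent.

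**Step 2: comparing experience levels.** With m polyps per endoscopist, the design effect is DE = 1 + (m − 1) × ICC, and the actual alpha is 2 × [1 − Φ(1.96/√DE)].

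| Polyps | Endoscopists | m | DE at ICC 0.02 / 0.05 / 0.10 | Actual alpha |
|---|---|---|---|---|
| 200 | 14 | 14.3 | 1.27 / 1.66 / 2.33 | 0.081 / 0.129 / 0.199 |
| 200 | 21 | 9.5 | 1.17 / 1.43 / 1.85 | 0.070 / 0.101 / 0.150 |
| 200 | 28 | 7.1 | 1.12 / 1.31 / 1.61 | 0.064 / 0.086 / 0.123 |
| 588 | 14 | 42 | 1.82 / 3.05 / 5.10 | 0.146 / 0.262 / 0.385 |
| 588 | 21 | 28 | 1.54 / 2.35 / 3.70 | 0.114 / 0.201 / 0.308 |
| 588 | 28 | 21 | 1.40 / 2.00 / 3.00 | 0.098 / 0.166 / 0.258 |

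Of the 588 polyps, only accuracy uses all; sensitivity, specificity, NPV and PPV each use a subset.

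**Step 3: simulation of both readings under no true effect.** Beta-binomial, 20 endoscopists with 28 polyps each, half in each arm, mean accuracy 0.80, 20,000 runs. At ICC 0.02, 0.05 and 0.10:

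- Chi-square between experience levels: false-positive rate 0.116, 0.202 and 0.313, in line with Step 2.
- Chi-square between arms within a level: 0.048, 0.043 and 0.041. When endoscopists work in both arms, their differences largely cancel, so there is no inflation.

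**Step 4: clustering within patients.** For all polyps, 588/168 = 3.5 per patient. At an assumed patient ICC of 0.05-0.30, DE is 1.13-1.75 and actual alpha 0.065-0.138. For the 200 target polyps, 200/168 = 1.19 per patient, and actual alpha is at most 0.057. This source matters only where a patient contributes several polyps to the measure.

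**Step 5: separate tests with an identical effect.** Take 75% v 90% in both levels. Power per level = Φ{[0.15 − 1.96 × √(2 × 0.825 × 0.175/n)] / √(0.2775/n)}, with n per arm per level.

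- 200 polyps, n = 200/4 = 50: (0.15 − 1.96 × 0.0760)/0.0745 = 0.014, power 0.506. Exactly one level significant: 2 × 0.506 × 0.494 = 0.50.
- 588 polyps, n = 588/4 = 147: (0.15 − 1.96 × 0.0443)/0.0434 = 1.453, power 0.927. Exactly one level significant: 2 × 0.927 × 0.073 = 0.14.

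**The case against.** The strongest reply is that the protocol sets out neither test. It does not say that experience levels are tested against each other, that arms are tested within levels, or that a subgroup claim will follow. Section 14.2 also provides for description, and units, cut-points and interaction terms are commonly left to the SAP, which is not shown. Much of this stands: the two readings are inferences about how the rule would be applied. But the descriptive sentence covers only the percentage of polyps correctly identified, which is accuracy at most. It does not mention experience and exempts nothing from the Chi-square rule. The point is therefore not that detail is missing. A method is stated, without exception, that does not fit this endpoint, and an SAP that used a model would depart from it.

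Three stronger readings are tempting, and the document does not support them.

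- *The rule is wrong however it is applied.* It is not. Under the assumption that endoscopists work in both arms, endoscopist clustering leaves the arm comparison within a level at or just below 5%. Patient-level randomisation stratified by site suggests such working but does not guarantee it. That test goes wrong only when two p-values are read as an interaction.
- *False experience effects are likely.* Even the top of the range, 39%, is below one half, and it needs the fewest endoscopists, the highest ICC and all 588 polyps together.
- *The trial's central rationale depends on this analysis.* The wording on non-expert and expert level in Section 10 concerns ADR under CADe. The objectives in Section 7.2 break performance down by size, location and morphology, not experience.

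**Conclusion.** The concern holds in limited form. Read literally, Section 14.2 assigns a polyp-level test of independence to a breakdown by an endoscopist-level factor, and that test cannot show whether the CADx effect depends on experience.

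A comparison of levels exceeds its nominal 5% throughout the range examined, but by how much depends on the number of endoscopists and the ICC, neither of which the protocol gives. For comparisons within levels, the defect is the absent interaction, not inflation from endoscopist clustering. How often the levels then disagree depends heavily on the polyp count and on the assumed equal split. AUC lies outside the rule. This is one secondary endpoint, and nothing here affects the primary ADR comparison.

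**What to change.** State in Section 14.2 that diagnostic performance by endoscopist experience is exempt from the Chi-square rule, and replace it as follows.

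- **Binary measures:** one cluster-adjusted logistic model per measure (GEE or mixed), with arm, lifetime procedures, their interaction and site. Clustering is by endoscopist, and also by patient where patients contribute several polyps. With about 1.2 target polyps per patient, a patient term for diminutive rectosigmoid polyps would be weakly identified and may be left out there.
- **Reporting:** the interaction estimate with its confidence interval, and no significance claims within single experience levels.
- **AUC:** descriptive by experience, with a cluster-based interval.

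If only description was intended, saying so for this endpoint and dropping level-wise p-values would also resolve the point.

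The cost is wording and modest analysis work. Section 11.4 already records the endoscopist and lifetime procedures, so no new data are needed. The downside is wider intervals and, with few endoscopists, an imprecise interaction estimate. It is best done before analysis, since Section 14.4 sends later deviations to the Trial Steering Committee and substantial ones to the ethics committee.

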# 14.3 Procedure for Dealing with Missing, Unused and Spurious Data

We expect very little missing data due to non-response given the nature of the intervention in this study. If the amount of missing data is not significant, we will use listwise deletion (i.e. only subjects with complete data will be included in the full ITT primary analysis). If the amount of missing data is significant, we will use standard statistical/imputation methods to deal with that and minimise data loss.

